3.0	12Jul2022	
 - Correction per Clinical Trial Protocol amendment 3 in Section 5.9 - Clarifications in Section 5.1 	
 - Align with Clinical Trial Protocol amendment 3 - Clarifications for programming derivation
4.0	28Nov2022	
 - Correction per Clinical Trial Protocol amendment 4 - Modify PPI definition and derivation (to remove PPI2) - Add further output by SARS-CoV-2 Status at Baseline 	
 - Align with Clinical Trial Protocol amendment 4 - Only define one PPI population including all subjects eligible at study entry - Clarifications for programming derivation
5.0	06Sep2023	
 - Remove the use of MSD results to derive the serostatus at baseline - Add sensitivity analysis on S-ELISA, excluding samples after a 2-fold increase in N-ELISA concentrations is detected - Add shift table for laboratory parameters 	
 - MSD was not fit for purpose at the time of PA and therefore the data were not used to derive the serostatus at baseline. The same approach is then taken for FA, and MSD-4plex data will be reported descriptively as part of the exploratory assessments- Additional analysis excluding subjects with potential SARS-COV-2 infection - Further explore laboratory result changes over time

1. INTRODUCTION

This statistical analysis plan (SAP) specifies definitions of analysis sets, key derived variables, and the statistical analysis methods for the planned analyses of safety, reactogenicity, and immunogenicity data in addition to the planned analyses of the study. The SAP (version 4.0) is based on Clinical Trial Protocol VAC31518COV3006 (CTP) Amendment 4. Previously, this study was designed to comprise Part 1 and Part 2, wherein Part 2 included the Extension Cohort of vaccine naïve participants for evaluation of the dose level and dose regimen selected after review of the data in Part 1. Per CTP amendment 4, Part 2 will no longer be conducted. This SAP therefore refers to Part 1 only. Data from participants who solely received placebo based on CTP Amendment 1 will only be listed. Titles, mock-ups and programming instructions for all statistical outputs (tables, figures and listings) will be provided in a separate document, the Data Presentation Specifications (DPS). This SAP will be finalized prior to the database lock for the primary analysis. After the database lock, separate SAP document(s) may be written as needed to cover specific unplanned analyses that cannot be documented elsewhere (e.g. in the DPS document).

1.1. Objectives and Endpoints

Part 1: Objectives and Endpoints

Objectives	Endpoints
Primary	

 To assess the safety and reactogenicity of Ad26.COV2.S administered intramuscularly as a 1-dose regimen (at 2.5×10^{10} vp per 0.25 mL, 1.25×10^{10} vp, and 0.625×10^{10} vp dose level) or as a 2-dose (56-day interval) regimen (2.5×10^{10} vp per 0.5 mL, 1.25×10^{10} vp, and 0.625×10^{10} vp dose levels) in adolescents. 	
 Solicited local and systemic adverse events (AEs) for 7 days post-dose 1 and 2. Unsolicited AEs for 28 days post-dose 1 and 2. Medically-attended adverse events (MAAEs) from the first vaccination until 6 months post-dose 1 or post-dose 2. MAAEs leading to discontinuation will be collected during the entire study. Serious adverse events (SAEs) from the first vaccination until the end of the study. Adverse events of special interest (AESIs) from first vaccination until end of the study (incl. multisystem inflammatory syndrome in children [MIS-C]).

 To assess the humoral immune response of Ad26.COV2.S administered IM as a 1-dose regimen (at 2.5×10^{10} vp per 0.25 mL, 1.25×10^{10} vp, and 0.625×10^{10} vp dose level) or as a 2-dose (56-day interval) regimen (2.5×10^{10} vp per 0.5 mL, 1.25×10^{10} vp, and 0.625×10^{10} vp dose levels) in adolescents. 	
 Serological response to vaccination as measured by spike-enzyme-linked immunosorbent assay (S-ELISA) (ELISA; Units/mL [EU/mL]) or equivalent assay, or virus neutralization assay (VNA) titers at 28 days post-dose 1 and 14 days post-dose 2.

Secondary and Exploratory Objectives and Endpoints for Part 1

Secondary	

 To assess the humoral immune response to 3 dose levels of Ad26.COV2.S (2.5×10^{10} vp, 1.25×10^{10} vp or 0.625×10^{10} vp) and regimens in all study groups at all blood collection timepoints. 	
 Serological response to vaccination measured by binding antibody titers to SARS-CoV-2 or individual SARS-CoV-2 proteins (e.g, S protein) as measured by ELISA (or equivalent assay), and/or Serological response to vaccination measured by neutralizing antibody titers to SARS-CoV-2 (VNA).

 To assess the safety and reactogenicity of Ad26.COV2.S administered IM as a booster in adolescent participants (Groups 1-3). 	
 Solicited local and systemic AEs for 7 days post-booster. Unsolicited AEs for 28 days post-booster. MAAEs from the booster until 6 months post-vaccination.

 To evaluate the humoral immune response in adolescent participants who receive a booster dose during the study, pre-boost and at selected time points post booster vaccination (Groups 1-3). 	
 Serological response to vaccination measured by binding (S-ELISA and/or equivalent assay) and/or neutralizing (VNA) antibody titers

Exploratory	

 To examine the immune response in vaccinated adolescents after SARS-CoV-2 infection. 	
 Confirmation of SARS-CoV-2 infection by molecular testing.⁽¹⁾ SARS-CoV-2 neutralizing titers in serum measured by a VNA.⁽¹⁾ SARS-CoV-2-binding antibodies measured by ELISA (or equivalent assay): Analysis of antibodies binding to the SARS-CoV-2 S and/or N protein.⁽¹⁾ Analysis of gene expression by ribonucleic acid (RNA) transcript profiling in adolescents.⁽¹⁾

 To assess the correlation between the binding antibodies (S-ELISA) and neutralizing antibody (VNA) titers to SARS-CoV-2 at selected timepoints. 	
 Correlation between ELISA (S-ELISA; EU/mL, or equivalent assay) and VNA (wtVNA⁽¹⁾ and/or psVNA) titers at selected timepoints.

 To assess the occurrence of symptomatic molecularly confirmed COVID-19 and severity of COVID-19 signs and symptoms in adolescents. 	
 The number of adolescents with molecularly confirmed COVID-19.⁽¹⁾ Presence and severity of COVID-19 signs and symptoms as measured by the Symptoms of Infection with Coronavirus-19 (SIC).

 To assess for the occurrence of asymptomatic SARS-CoV-2 infection. For Asymptomatic case definition: See CTP Section 10.9.3 	
 Serologic conversion between baseline (Day 1; pre-vaccination) and selected timepoints post-vaccination using an ELISA and/or SARS-CoV-2 immunoglobulin assay that is dependent on the SARS-CoV-2 N protein The number of asymptomatic participants with a SARS-CoV-2 positive molecular test.

Exploratory	

 To assess the impact of pre-existing humoral immunity against coronaviruses other than SARS-CoV-2 at baseline on Ad26.COV2.S vaccine immunogenicity. 	
 Analysis of antibodies binding to coronaviruses other than SARS-CoV-2 by ELISA or equivalent assay. ⁽¹⁾

 To assess the impact of the Ad26.COV2.S vaccine on the incidence of co-infections with SARS-CoV-2 and other respiratory pathogens in adolescents who have received Ad26.COV2.S during the study. 	
 Analysis of broad respiratory pathogens panel in the nasal swabs collected during a confirmed COVID-19 episode and in nasal swab samples from adolescents with a symptomatic infection. ⁽¹⁾

 To assess the presence of SARS-CoV-2 variants during a confirmed COVID-19 episode in adolescents. To assess SARS-CoV-2 viral load during a confirmed COVID-19 episode in adolescents. 	
 Identification of SARS-CoV-2 variants by sequencing of nasal swabs and/or saliva samples (as available) collected during a confirmed COVID-19 episode. ⁽¹⁾ Analysis of SARS-CoV-2 viral load (via qRT-PCR) in nasal swabs and/or saliva samples (as available) collected during a confirmed COVID-19 episode. ⁽¹⁾

 To further explore the humoral immune responses in participants who have received Ad26.COV2.S. 	
Exploratory analyses may include the following assays:
 
Humoral Immune Response:
 
 SARS-CoV-2 neutralization as assessed by VNA. Adenovirus neutralization as measured by VNA. ⁽¹⁾ Analysis of neutralizing and binding antibodies⁽¹⁾ against emerging SARS-CoV-2 virus lineages. Functional and molecular antibody characterization including, but not limited to avidity, Fc-mediated viral clearance, Fc characteristics, Ig subclass and IgG isotype, antibody glycosylation, and assessment of antibody repertoire. ⁽¹⁾ Analysis of antibodies to S, N, and the receptor binding domain (RBD) of the SARS-CoV-2 S protein, and surface proteins of other coronaviruses. ⁽¹⁾ Epitope-specificity characterization of antibodies. ⁽¹⁾ Cytokine profiling: Analysis of cytokines, chemokines, and other proteins of the innate or adaptive immune response in the serum or plasma. ⁽¹⁾ Passive transfer: Analysis of immune mediators correlating with protection against experimental SARS-CoV-2 challenge in a suitable animal model. ⁽¹⁾ Seroresponse rates according to different responder definitions.

⁽¹⁾ May be considered as potential assessment for analyses after the primary analysis is performed.

1.2. Study Design

This is a randomized, observer-blind, pivotal Phase 2 study in healthy adolescents from 12 to 17 years of age. The safety, reactogenicity, and immunogenicity of Ad26.COV2.S in a 1- and 2- active dose (56-day interval) vaccination regimen will be evaluated.

The study will descriptively compare the immune responses measured by S-ELISA (and potentially VNA) in adolescents versus the immune responses measured in young adults from study VAC31518COV3001 (after administration of 1 dose of Ad26.COV2.S) or VAC31518COV3009 (after administration of 2 doses of Ad26.COV2.S) and between study groups in VAC31518COV3006.

Previously, this study was designed to comprise Part 1 and Part 2, wherein Part 2 included the Extension Cohort of vaccine naïve participants for evaluation of the dose level and dose regimen selected after review of the data in Part 1. Per CTP amendment 4, Part 2 will no longer be conducted. The study therefore consists of a Dose Selection Cohort to select the most appropriate dose level and regimen for adolescents of 12 to 17 years of age.

The COV3006 study evaluates different dose regimen (1 or 2 vaccinations) and dose levels of 2.5×10^{10} vp and lower in participants from 12 to 17 years of age. The 2.5×10^{10} vp has been tested before, in study VAC31518COV2001. A single dose of Ad26.COV2.S at 2.5×10^{10} vp was administered to a cohort of participants 16 to 17 years of age (33 participants received active vaccine or placebo in a blinded manner, 10:1 ratio). Immunogenicity and safety data in adolescents 16 to 17 years of age and adults from COV2001 were evaluated by an IDMC and the Medicines and Healthcare products Regulatory Agency who allowed a continuation of evaluation in participants of 12 to 15 years of age.

In Part 1 (since CTP amendment 2), a target of approximately 300 adolescents, seronegative for SARS-CoV-2 antibodies at baseline will be enrolled to receive 2 vaccinations in the primary vaccination regimen (56-day interval). This primary vaccination regimen will contain 1 or 2 active vaccinations, 1st vaccination with active vaccine for all and second with either active vaccine with the same dose level as 1st or placebo. In this way different doses and schedules (1 or 2 vaccination regimen with active vaccine) will be explored. In Part 1, per CTP amendment 1, some subjects were also randomized to receive placebo only (and were withdrawn by CTP amendment 2).

Since CTP amendment 2, the study starts with a Dose Selection Cohort (Part1), where the participants will be randomly assigned in a 1:1:1:1:1:1 ratio to 1 of 3 study arms to receive one active vaccination of Ad26.COV.2 (either 2.5×10^{10} vp per 0.25 mL dose volume, 1.25×10^{10} vp, or 0.625×10^{10} vp) followed by placebo in a 1-(active) dose regimen (Groups 1, 2 and 3, respectively), or 1 of 3 study arms to receive the same dose level of 2.5×10^{10} vp (per 0.5 mL dose volume), 1.25×10^{10} vp, or 0.625×10^{10} vp in a 2-(active) dose (56-day interval) regimen (Groups 4, 5 and 6, respectively). Each study group will contain approximately 50 participants. Since CTP amendment 3, approximately 70% will be 12 to 15 years of age and approximately 30%, 16 to 17 years of age. Adolescents will be unblinded to the primary vaccination regimen at 6 months after the first vaccination. Also, participants in Groups 1-3 will be given a booster vaccination as of 6 months after the last vaccination with active vaccine. The booster dose level will be 2.5×10^{10} vp per 0.5 mL. Participants in Groups 4-6 will be not given a booster vaccination in the study.

The vaccination schedule for Part 1 is displayed in [Table 1](#).

As a part of the COVID-19 program safety oversight, the IDMC will review the data on an ongoing basis, in addition to two study-specific predefined IDMC analyses.

Table 1: Part 1 Vaccination Schedules (Dose Selection Cohort)

Group	N^{a,b,c}	Vac 1	Vac 2	Vac 3
		Day 1	Day 57	Day 184
1	50	2.5×10^{10} vp (0.25 mL)	Placebo	2.5×10^{10} vp (0.5 mL)
2	50	1.25×10^{10} vp	Placebo	2.5×10^{10} vp (0.5 mL)
3	50	0.625×10^{10} vp	Placebo	2.5×10^{10} vp (0.5 mL)
4	50	2.5×10^{10} vp (0.5 mL)	2.5×10^{10} vp (0.5 mL)	none
5	50	1.25×10^{10} vp	1.25×10^{10} vp	none
6	50	0.625×10^{10} vp	0.625×10^{10} vp	none

N = number of participants; n/a = not applicable; SDL = selected dose level; Vac = vaccination; vp = virus particles.

a Not more than 70% of males or females should be randomized in each age group

b All participants must be seronegative for SARS-CoV-2 antibodies at baseline.

c Approximately 30% of participants should be between 16 to 17 years age and approximately 70% should be between 12 to 15 years of age.

Not more than 70% males or females will be randomized in each age group. The randomization will be stratified by sex and age group. In Part 1, screening will aim to ensure participants are seronegative at baseline for SARS-CoV-2 antibodies.

The end of study is considered as the last visit shown in the Schedule of Activities for the last participant in the study.

2. STATISTICAL HYPOTHESES

There is no formal hypothesis testing in Part 1.

Descriptive statistics will be reported to descriptively compare vaccine immunogenicity in adolescents from this study VAC31518COV3006 versus vaccine immunogenicity in selected young adults (18 to 25 years of age) from study VAC31518COV3001 or study VAC31518COV3009 (with similar baseline characteristics to the participants expected to be enrolled in this study – see Section 6.11), and between study groups in VAC31518COV3006.

All enrolled participants were seronegative for SARS-CoV-2 antibodies when screened with local rapid finger-prick serology testing at baseline. However, the primary analysis results have shown that many participants were retrospectively established to be SARS-CoV-2 seropositive at baseline by central testing with Nucleocapsid (N) and/or Spike (S) -based serology. Therefore data from SARS-CoV-2 seropositive young adult (18 to 25 years of age) selected from other Phase 3 studies will be used to compare vaccine immunogenicity in seropositive at baseline adolescents from this study.

3. SAMPLE SIZE DETERMINATION

The sample size for Part 1 shall enable selection of appropriate doses and regimens. Decision making on the optimal regimen will primarily take into account safety and reactogenicity data. Non-binding guidelines on dose and regimen selection are described in Section 5.9.1.

Additionally, any available immunogenicity data from Part 1 participants and data from other Janssen clinical trials of Ad26.COV2.S will also be considered.

With a sample size of 50 participants per study group, the width of the 90% CI for the observed proportion of adverse events will vary between 5.8% and 24.8% depending on the observed proportion. Assuming pooling of adverse event data after the first active dose on the same dose level of the 1- and 2-dose regimen, the width of this confidence interval will vary between 3% and 17.3% depending on the observed proportion ([Table 2](#)).

Table 2: 90% Two-Sided CI for Possible Observed Rate of Adverse Events

Observed Rate	0%	5%	10%	25%	50%
50 Participants	(0, 5.8%)	(1.2%, 13.4%)	(4%, 19.9%)	(15.3%, 37%)	(37.6%, 62.4%)
100 Participants	(0, 3%)	(2%, 10.2%)	(5.5%, 16.4%)	(18%, 33.1%)	(41.4%, 58.6%)

In Part 1, a target of approximately 300 adolescents, seronegative for SARS-CoV-2 antibodies at baseline will be enrolled.

4. POPULATIONS (ANALYSIS SETS) FOR ANALYSIS

Analysis Sets	Description
Enrolled	All participants who sign the main ICF.
Randomized	The randomized analysis set includes all participants who were randomized in the study.
Full Analysis Set (FAS)	The Full Analysis Set will include all participants with at least one vaccine administration documented.

Analysis Sets	Description
Per Protocol Immunogenicity Set (PPI) ^a	The Per Protocol Immunogenicity population will include all randomized and vaccinated participants for whom immunogenicity data are available excluding data from participants with major protocol deviations expected to impact the immunogenicity outcomes (see details in Section 6.3). In addition, samples obtained after missed vaccinations, samples obtained from participants after SARS-CoV-2 infection (if confirmed by molecular testing or non-S-ELISA [or equivalent assay]), occurring during the study after randomization (if applicable), after other SARS-CoV-2 vaccination outside the study, and samples obtained outside pre-defined time windows will be excluded from the analysis set (see details in Sections 5.1.4 and 6.3).

^a If a participant is vaccinated out of window due to a study pause, this will not by default be a reason for excluding this participant from the PPI. Participants who were seronegative by local serology finger-prick test on Day 1 prior to study entry but were determined to be seropositive at baseline by central N- or S- serology testing will also be included (as the results from those assessments are not known prior to randomization).

5. STATISTICAL ANALYSES

5.1. General Considerations

Details of the vaccine schedules associated to the primary vaccine regimen will be provided in the data presentation specification (DPS) document. Vaccination schedule have 2 components:

- Primary Vaccine Regimen (1-active dose or 2-active dose)
- Booster Vaccination (i.e. after unblinding)

Unless specified otherwise, analyses outputs will be produced by age group (12 to 15, 16 to 17, and overall). Where applicable, output will include results by dose level (1-active dose regimen and 2-active dose regimen combined) to report the post-dose 1 period.

All safety and immunogenicity data after a participant has received any other SARS-CoV-2 vaccine not part of the protocol will not be tabulated. Those data will be in listings.

A baseline (or reference) value will be defined as the value of the last available assessment prior to the first vaccination on Day 1, unless specified otherwise.

Unless otherwise stated, safety analyses will be conducted on the FAS, Immunogenicity analyses on the PPI.

5.1.1. Study Day and Relative Day

Study Day 1 or Day 1 refers to the start of the first study vaccination. Unless specified otherwise, safety assessments at all visits will be assigned a day relative to this date. In addition, safety assessments occurring after vaccination 2 in the primary regimen period and those occurring after the booster vaccination date will also be assigned a day relative to those dates.

Study Day is defined as follows:

- *Study Day=visit date-date of Day 1 + 1; if visit date \geq date of Day 1 (date of first vaccination).*
- *Study Day=visit date-date of Day 1; if visit date < date of Day 1 (date of first vaccination).*

Relative day (relday), the number of days in the analysis time point will be defined as:

- *relday=visit date-reference date+1 for visits on or after the reference date,*
- *relday=visit date-reference date for visits before the reference,*

where the reference date equals the date of vaccination 1 or 2, or the date of booster vaccination.

5.1.2. Study Phases

To assess study phases, in case the time of the vaccination is missing, the time will be imputed with 00:00 before applying the phase and period derivation rules. When the time of the first vaccination is missing and it occurred on the same day as the randomization, the time of vaccination will be imputed with the time of randomization.

The safety analysis results will be presented by phase/period.

5.1.3. Phase Definitions

The phases in the Part 1 will be constructed as described in [Table 3](#).

Table 3: Phase Definitions

Phase	Phase #	Period	Period #	Interval	
				From	To
Screening	1			Date and time of signing the IC form	One second prior to start of post dose 1 period
Post-dose	2	Post-dose 1	1	Date and time of first vaccination	
Minimum of:
 
 a) 23:59:59 at the date of last contact (for early discontinuation) b) 23:59:59 at the date of data base cut-off date in case of interim analysis c) 23:59:59 on 28 days after the first vaccination (23:59:59 of day of vaccination + 28 days) d) One second prior to date and time of second vaccination e) One second prior to date and time of Booster Vaccination f) One second before date and time of another viral vaccination outside the study
Follow-up 1	3			One second after Post-dose 1 period end	
Minimum of:
 
 a) 23:59:59 at the date of last contact (for early discontinuation) b) 23:59:59 at the date of data base cut-off date in case of interim analysis c) One second prior to 6 months after first vaccination (vaccination date + 6 mths) d) One second prior to date and time of second vaccination e) One second prior to date and time of Booster Vaccination f) One second before date and time of another viral vaccination outside the study
Post-dose	2	Post-dose 2	2	Date and time of second vaccination	
Minimum of:
 
 a) 23:59:59 at the date of last contact (for early discontinuation) b) 23:59:59 at the date of data base cut-off date in case of interim analysis c) 23:59:59 on 28 days after the second vaccination (23:59:59 of day of vaccination + 28 days) d) One second prior to date and time of Booster Vaccination e) One second before date and time of another viral vaccination outside the study

Table 3: Phase Definitions

Phase	Phase #	Period	Period #	Interval	
				From	To
Follow-up 2	4			One second after Post-dose 2 period end	
Minimum of:
 
 a) 23:59:59 at the date of last contact (for early discontinuation) b) 23:59:59 at the date of data base cut-off date in case of interim analysis c) One second prior to 6 months after second vaccination (vaccination date + 6 mths) d) One second prior to date and time of Booster Vaccination e) One second before date and time of another viral vaccination outside the study
Long term follow-up	5			One second after Follow-up 1 if only 1 dose was administered, and one second after Follow-up 2 if the 2 doses were administered	
Minimum of:
 
 a) Maximum of 23:59:59 at the date of last contact (for early discontinuation) and 23:59:59 at the date of last visit b) 23:59:59 at the date of data base cut-off date in case of interim analysis a) One second prior to date and time of Booster Vaccination b) One second before date and time of another viral vaccination outside the study c) One second prior to end of the study visit
Post-dose	2	Post-dose 3 (will be referred as Post-booster in the output)	3	Date and time of Booster Vaccination	
Minimum of:
 
 a) 23:59:59 at the date of last contact (for early discontinuation) b) 23:59:59 at the date of data base cut-off date in case of interim analysis c) 23:59:59 on 28 days after the Booster Vaccination d) One second before date and time of another viral vaccination outside the study
Booster follow-up 1	6			One second after Post-dose 3 period end	
Minimum of:
 
 a) 23:59:59 at the date of last contact (for early discontinuation) b) 23:59:59 at the date of data base cut-off date in case of interim analysis c) One second prior to 6 months after Booster Vaccination d) One second before date and time of another viral vaccination outside the study
Booster long term follow-up	7			One second after booster follow-up 1	
Minimum of:
 
 a) Maximum of 23:59:59 at the date of last contact (for early discontinuation) and 23:59:59 at the date of last visit b) 23:59:59 at the date of data base cut-off date in case of interim analysis c) One second before date and time of another viral vaccination outside the study d) One second prior to end of the study visit

Table 3: Phase Definitions

Phase	Phase #	Period	Period #	Interval	
				From	To
Follow-up other vaccine	8			Date and time of viral vaccination outside the study	Minimum of: a) Maximum of 23:59:59 at the date of last contact (for early discontinuation) and 23:59:59 at the date of last visit b) 23:59:59 at the date of data base cut-off date in case of interim analysis c) Date and time of end of the study visit

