10.2. Appendix 2: AESI Clinical Laboratory Tests

Samples will be taken according to the SoA in Section 1.3. The following tests may be performed:

Protocol-Required AESI Laboratory Assessments

Laboratory Assessments	Parameters for Participants Evaluated at Prespecified Study Timepoints and, in Addition, upon Experiencing a Suspected AESI
Performed locally (or centrally if local laboratory is not available)	
	Blood sample obtained and tested at study Day 1, Day 29, Day 57, Day 71 (for all participants), for visits Day 184 and Day 198 (for Groups 1-3), AND Day 1/29 for each occurrence of any suspected AESI (TTS and/or MIS-C)
Hematology	Whole blood sample for platelet count which at some sites may be part of a complete blood count with differential.
Suspected TTS AESI	
Stored and performed centrally	
Only analyzed if participant experienced suspected TTS, upon request from central study team: Blood sample obtained at Day 1/29 for each occurrence of suspected TTS AESI and for visits Day 1, Day 29, Day 57, Day 71 (for all participants), for visits Day 184 and Day 198 (for Groups 1-3)*.	
Clinical Laboratory Assessments (Section 8.2.4.1)	
Serum/plasma samples for coagulation-related assays such as but not limited to:
 
 • Activated partial thromboplastin time • Prothrombin time • International normalized ratio • Fibrinogen • Lupus anticoagulant • Beta-2 glycoprotein • Anti-cardiolipin • D-dimers • Anti-PF4 • Heparin Induced Thrombocytopenia (HIT)/PF4 Ab, IgG·(HIT assay) • Platelet activation assay (if HIT/PF4 is positive) • Homocysteine • ADAMTS13 Activity and Inhibitor Profile

Laboratory Assessments	Parameters for Participants Evaluated at Prespecified Study Timepoints and, in Addition, upon Experiencing a Suspected AESI
Suspected MIC-S AESI Stored and performed centrally: Only analyzed if participant experienced suspected MIS-C, upon request from central study team: Blood sample obtained at Day 1/29 for each occurrence of suspected MIS-C AESI and for visits Day 1, Day 29, Day 57, Day 71 (for all participants), for visits Day 184 and Day 198 (for Groups 1-3)*.	
Clinical Laboratory Assessments (Section 8.2.4.2)	
 • Serum/plasma samples for coagulation-related assays such as, but not limited to, D-dimers • Levels of inflammatory markers in the blood, including elevated ESR/CRP and ferritin, LDH, and ALC • B-type natriuretic peptide (BNP) or NT-proBNP (pro-BNP) • Sodium

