5.7.2. Laboratory, Vital Signs and Physical Examination

Coagulopathy laboratory values will be listed. A listing of all other laboratory values will be made, restricted to participants with at least one laboratory abnormality.

Physical examination findings will be summarized at baseline. A listing of the abnormalities will be made.

Vital signs including temperature, pulse/heart rate, respiratory rate, and blood pressure (systolic and diastolic) will be summarized over time, using descriptive statistics.

Abnormalities emerging after vaccination will be tabulated by worst abnormality grade using the FDA table in Section 6.8 and in Section 6.9.

An abnormality (toxicity grade or abnormality based on normal ranges) will be considered as emerging in a particular period if it is worse than the baseline value. If the baseline is missing, the abnormality is always considered emerging. A shift from ‘abnormally low’ at baseline to ‘abnormally high’ post baseline (or vice versa) is also considered emerging. In case a laboratory test result is censored (no numeric value is available, but only a verbatim term) then a numeric value will be imputed by a value exceeding the cut-off value with one unit. (<x: subtract 1 unit from x, >x: add 1 unit to x; <3.45 is imputed with 3.44).

In case no toxicity grades are defined for a test, the abnormalities (above/below normal range) will be used. In determining toxicity grades, the following rules are applied:

- Worst grades/abnormalities are determined over the whole observational period for each trial period separately, including all post-baseline measurements of that period.
- The abnormalities ‘abnormally low’ and ‘abnormally high’ are considered equally important, i.e. if a participant has as well an abnormally low as an abnormally high value post-baseline, both abnormalities are shown in the tables. (This means that the sum of the percentages can be more than 100%).

- Note: as the grading scale for some parameters in the grading table has some gaps (zones where no toxicity grade definition exists), laboratory results falling in these zones will be allocated to the adjacent worst-case grade.
- If a laboratory value falls within the grading as specified in the grading table but also within the local lab normal limits, the value is considered as normal.

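### Post-dose 1 closes on Study Day 29, but its only scheduled laboratory draw is allowed up to Day 32, so late in-window samples are counted in Follow-up 1 in the by-period laboratory tables

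*SAP*

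**What the plan says.** SAP 5.1.3, Table 3, ends Post-dose 1 (absent an earlier event such as discontinuation or another vaccination) at "23:59:59 on 28 days after the first vaccination (23:59:59 of day of vaccination + 28 days", and Follow-up 1 begins "One second after Post-dose 1 period end". The corresponding limits after dose 2 and the booster are "23:59:59 on 28 days after the second vaccination (23:59:59 of day of vaccination + 28 days" and "23:59:59 on 28 days after the Booster Vaccination". Days are counted by SAP 5.1.1: "Study Day=visit date-date of Day 1 + 1".

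SAP 5.1.2 states: "The safety analysis results will be presented by phase/period". For laboratory data, SAP 5.7.2 adds: "Worst grades/abnormalities are determined over the whole observational period for each trial period separately, including all post-baseline measurements of that period". An abnormality is likewise judged to be emerging within a particular period.

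Protocol Appendix 2 (10.2) lists the haematology draws: "Blood sample obtained and tested at study Day 1, Day 29, Day 57, Day 71 (for all participants", with Days 184 and 198 added for Groups 1-3. The Schedules of Activities (Protocol 1.3.1 and 1.3.2) give Visit 4 a window of Day 29 ± 3.

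**The concern.** The period boundary falls on the target day of the visit, so the second half of the visit window lies outside the period that the visit is meant to describe. A participant can attend within protocol and still contribute no scheduled laboratory value to Post-dose 1. The sample is instead counted in Follow-up 1 with the Day 57 pre-dose 2 sample.

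Post-dose 1 is a main reporting unit: SAP 5.1 combines the 1-dose and 2-dose regimens by dose level to report it. The SAP does not state the denominator of the by-period laboratory tables. If it is everyone vaccinated, participants sampled late count as having no abnormality in Post-dose 1. If it is those with a value, the denominator shrinks with visit timing.

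**Working it through.** **Day rule.** SAP 5.1.1 makes the relative day equal to date minus reference date plus 1. It reproduces the protocol's target days:
- Dose 1 on Day 1: +28 days gives Day 29, and +56 gives Day 57.
- Dose 2 on Day 57: +7, +14 and +28 days give Days 64, 71 and 85.
- Booster on Day 184: +7, +14 and +28 days give Days 191, 198 and 212.

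**Period end.** Vaccination day + 28 days is relative day 28 + 1 = 29. Follow-up 1 therefore starts at 00:00:00 on Day 30.

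**Draw windows against that limit.**

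| Laboratory draw | Counted from | Window | Relative days | Days after relative day 29 |
|---|---|---|---|---|
| Visit 4 | dose 1 | Day 29 ± 3 | 26 to 32 | 30, 31, 32 (3 of 7) |
| Visit 5, before dose 2 | dose 1 | Day 57 −3/+7 | 54 to 64 | all (11 of 11) |
| Visit 7 | dose 2 | Day 71 ± 2 | 13 to 17 | none (0 of 5) |
| Visit 11 (Groups 1-3) | booster | Day 198 ± 3 | 12 to 18 | none (0 of 7) |

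The Visit 5 draw also follows dose 1, but in window it is always in Follow-up 1, so it cannot stand in for a late Visit 4 sample.

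**Is there a rule that moves the sample back?** SAP 5.1.4 opens with a general statement that protocol visit windows are considered where applicable, but its specific rules concern immunogenicity samples. The explicit allocation by start date in SAP 5.7.1.4 concerns adverse events. No rule in the SAP returns a Day 30 to 32 laboratory sample to Post-dose 1.

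**Size.** The share *s* of Visit 4 samples drawn on Days 30 to 32 is not in the documents. Samples moved = *s* × 300:

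| Assumed *s* | Of 300 | Average per group of 50 |
|---|---|---|
| 0% | 0 | 0 |
| 5% | 15 | 2.5 |
| 10% | 30 | 5 |
| 20% | 60 | 10 |
| 3/7 (uniform over the window) | about 129 | about 21 |

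Under allocation by nominal visit, or with the laboratory period run to Day 32, 0 of the 7 permitted days would fall outside.

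**The case against.** The strongest reply is that nothing disappears, and this stands. The shift table in SAP 5.7.2 is by timepoint. The Table 4 intervals that cover the primary regimen include Follow-up 1. Coagulopathy values are listed, as are all other laboratory values of any participant with an abnormality.

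It also stands that the 28-day limit is coherent for adverse events, since it matches the collection period for unsolicited events in Protocol 8.3.1. Programming detail sits in the Data Presentation Specifications, which are not among the documents, so an allocation rule may exist there. The SAP itself still gives the opposite result if followed as written.

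Four stronger readings are tempting but not supported:
- *Platelet falls would be missed.* A count below 150,000/µL is itself a suspected AESI (Protocol 8.3.6.1), recorded from vaccination to the end of the study. The mildest graded decrease in SAP Table 10 is 125,000 to 140,000, so every graded fall is below that threshold. Other blood count results, where sites run them, lack this second route.
- *The comparison between doses is biased by the cut.* No such laboratory contrast is planned, and safety is descriptive. The draw is 28 days after dose 1 but 14 days after dose 2 and the booster by design, so any such comparison reflects timing anyway. The six groups share one schedule up to Visit 8, so there is no evident reason for bias between them.
- *Some 43% of samples are affected.* That is the uniform case (3/7). Protocol section 8 tells sites to aim for the exact day and to use the window only when unavoidable.
- *Vital signs are equally exposed.* Visits 8 and 12 (Days 85 ± 3 and 212 ± 3) are cut in the same way as Visit 4. Earlier visits still supply values inside each period, and no period is singled out.

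**Conclusion.** The point holds in limited form. Following SAP 5.1.3 and 5.7.2 as written, any participant sampled in window on Days 30 to 32 has no scheduled laboratory value in Post-dose 1. Post-dose 2 and Post-booster cannot lose an in-window draw this way, although they remain subject to discontinuation, missed vaccination and vaccination outside the study.

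The effect is confined to the by-period emergent and worst-grade laboratory tables. A reader might infer that safety data are lost or that a platelet signal would be hidden; the documents support neither.

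The size depends wholly on late attendance: 0 to 60 of 300 samples for assumed shares of 0% to 20%, with about 129 as an upper illustration. The conclusion also assumes that laboratory samples are placed in periods by date. Table 3 implies this but does not say so expressly for laboratory data. The change is worth making because the tables would otherwise misplace results obtained fully within protocol.

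**What to change.** In SAP 5.1.3 and 5.7.2:
- State that scheduled laboratory assessments and, for consistency, vital signs are allocated to periods by nominal visit when they precede the next vaccination: Visit 4 to Post-dose 1, Visit 8 to Post-dose 2 and Visit 12 to Post-booster.
- Report the number of participants with a laboratory value in each period, and use it as the denominator of the by-period tables.
- Keep the 28-day cut for adverse event onset.

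The cost is a short addition to the SAP and a programming rule; no new data or visits are needed. The change does not remove the designed difference in draw timing (28 days after dose 1, 14 days after dose 2 and the booster), which a table footnote could state.
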